2.1.2 Primary Endpoints

Endpoints	Summary Measure
Subjects experiencing treatment-emergent adverse events (TEAEs) including: 
 • SAEs • AESIs • CSL312-induced ADAs • Clinically significant abnormalities in laboratory assessments that are reported as AEs 	Number and proportion of subjects experiencing the specified safety events after treatment with investigational product (CSL312 or placebo)

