8.1.1 Demographics and Safety Assessments

Subject demographics and safety assessments to be conducted during this study are provided in Table 7. Clinical laboratory assessments are to be performed at the time points indicated in the [Schedule of Assessments](#).

Table 7 Study Procedures: Demographics and Safety Assessments

Assessment	Description
Demographics	
 • Year of birth • Sex • Age • Race and ethnicity (where permitted)
Medical history	
 • Relevant medical history • Diagnosis and disease status • Contraception method (if relevant) • Previous (within 6 months before Screening) and concomitant medications and therapies
Pregnancy test (local laboratory)	A serum test for β -hCG will be performed for all female subjects of childbearing potential to rule out pregnancy at Screening. At all other study visits, a urine pregnancy test will be performed. If the results from the urine pregnancy test are inconclusive, the site will perform a serum pregnancy test.
Physical examination	As per the site's standard procedure, including assessment of unilateral pain and / or swelling of the lower extremities for the purposes of screening for DVTs.
12-lead ECG (Performed and analyzed locally)	
 • Heart rate • PR interval • QRS duration • Interpretation (investigator's overall interpretation) • QT interval • QTcB interval • QTcF interval
PFTs	
 • Spirometry including FVC and FEV₁ • DL_{CO}
AEs	
 • Evaluation of all AEs (eg, causality / relatedness, severity, seriousness) • AESIs: 
 ○ Abnormal bleeding events ○ TEEs ○ Severe hypersensitivity including anaphylaxis 
The description of AEs and reporting requirements are detailed in Section 9.

Vital signs	
 • Blood pressure (systolic and diastolic) • Respiratory rate • Heart rate • Body temperature • Height (Screening only) • Weight and BMI
Urinalysis (dipstick) (central laboratory)	
 • Specific gravity • pH • Nitrite • Ketones • Protein • Glucose • Occult blood • Leukocyte esterase • Erythrocytes • Bilirubin • Urobilinogen

Assessment	Description

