9.1.3 Adverse Event of Special Interest

There are several AEs that will be monitored closely as AEs of special interest (AESIs) to allow for an adequate risk-benefit evaluation of CSL312 during the study. Additional data may be requested for these events.

The AESIs for this study are:

- Bleeding events that are abnormal in the opinion of the investigator
- TEEs
 - Non-systemic thrombosis (eg, localized thrombosis associated with vascular access) is not considered an AESI
- Severe hypersensitivity including anaphylaxis

The reporting requirements for AESIs are detailed in [Section 9.6.2](#)

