9.6.2 Adverse Events of Special Interest

Adverse event of special interest must be reported as AEs in the subject's eCRF. Additional data may be requested in the eCRF for these events. Serious and nonserious AESIs must be reported following the procedures for expedited reporting as described for SAEs (see Section 9.6.3).

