11.2 Adverse Events

AEs will be coded using the MedDRA dictionary (the MedDRA version will be populated in the tables output). AEs will start to be collected upon the subject's signing of the informed consent form (ICF). TEAEs, defined as AEs starting on or after the date (and time if available) of the first administration of IP (IV loading dose) through the end of the Treatment and Observation Period, will be summarized. The summary will be given by treatment group and overall. All AEs regardless of whether they were treatment-emergent or not will be listed.

Where AE start dates and/or times are missing or partially missing, AEs will be assumed to be treatment-emergent, except if the partial start dates and/or times or the AE end date and/or time indicate that the AE started before the first administration of IP (Table 2).

Table 2 TEAE Assignment in Case of Missing AE Start Date Elements

Missing elements of AE start	Rule	
Regardless of any missing information for AE start: AE end date / time < IP start date / time		non TEAE
Otherwise (ie, if AE end date / time \geq IP start date / time)		
- all		TEAE
- day and month	AE start year \geq IP start year	TEAE
	AE start year < IP start year	non TEAE
- day	AE start month / year \geq IP start month / year	TEAE
	AE start month / year < IP start month / year	non TEAE
- time	AE start date \geq IP start date	TEAE
	AE start date < IP start date	non TEAE

If AE start dates or end dates are missing or partially missing for an AE, no duration will be calculated. A missing category will be shown in summary tables by severity in case the severity is missing (the same is applicable for relationship to study treatment). No imputations for missing AE information will be done.

The AESIs defined for this study are:

- Bleeding events - Standardised MedDRA Query "Haemorrhages (SMQ)" (narrow)
- Thromboembolic events (TEE) - Standardized MedDRA Query "Embolic and thrombotic events (SMQ)" (narrow) consisting of:

- Embolic and thrombotic events, arterial (SMQ);
 - Embolic and thrombotic events, venous (SMQ);
 - Embolic and thrombotic events, vessel type unspecified and mixed arterial and venous (SMQ).
- Severe Hypersensitivity including anaphylaxis - Standardised MedDRA Query “Hypersensitivity (SMQ)” (broad), “Anaphylactic reaction (SMQ)” (broad), and “Anaphylactic/anaphylactoid shock conditions (SMQ)” (broad). Here, broad scope includes narrow and broad search.

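### SAP 11.2 counts AESIs by MedDRA query alone: two Protocol 9.1.3 conditions are absent, severity is only a label, and the difference is not declared

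*SAP*

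**What the plan says.** Protocol 2.1.2 and SAP 4.1 (Table 1) both list AESIs within the primary endpoint, summarised as the number and proportion of subjects affected.

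Protocol 9.1.3 defines three categories. The first is "Bleeding events that are abnormal in the opinion of the investigator". The second is thromboembolic events (TEEs), with the carve-out "Non-systemic thrombosis (eg, localized thrombosis associated with vascular access) is not considered an AESI". The third is hypersensitivity that is severe, with anaphylaxis expressly included. Table 7 in Protocol 8.1.1 keeps the qualifier on the first category: "Abnormal bleeding events". Investigators must identify these events themselves, because under Protocol 9.6.2 "Serious and nonserious AESIs must be reported following the procedures for expedited reporting as described for SAEs".

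SAP 11.2 introduces its own list with "The AESIs defined for this study are" and gives only SMQ searches. Bleeding is the Haemorrhages query, narrow scope. TEE is the Embolic and thrombotic events query, narrow scope, with its three sub-queries. The third entry, "Severe Hypersensitivity including anaphylaxis - Standardised MedDRA Query", is followed by the hypersensitivity, anaphylactic reaction and anaphylactic/anaphylactoid shock queries, all broad, with the note "Here, broad scope includes narrow and broad search".

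SAP Table 1 lists bleeding events without the word abnormal. SAP section 5 says the planned analyses are unchanged and mentions only a modified Screened Analysis Set.

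**The concern.** An SMQ selects events by coded term. It does not use the investigator's opinion of whether a bleed was abnormal, nor the severity grade, which Protocol 9.2 has the investigator record separately for every adverse event. A count built on the search alone therefore answers a wider question than the protocol asks, and it need not agree with the AESIs that sites report under 9.6.2.

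The three categories correspond to the bleeding, thromboembolic and severe hypersensitivity risks described in Protocol 1.4.2. At stake is whether the headline AESI figure in the study report means what the protocol says it means, and whether a reader would know if it does not.

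**Working it through.** The documents give no expected AESI rate, so there is no planned figure to reproduce. The check is a comparison of definitions, followed by a scale calculation.

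**1. Definitions side by side**

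| Category | Protocol 9.1.3 condition | SAP 11.2 rule | Condition in SAP? |
|---|---|---|---|
| Bleeding | Investigator judges it abnormal | Haemorrhages SMQ, narrow | Absent; also absent from SAP Table 1 |
| TEE | Non-systemic thrombosis not counted | Embolic and thrombotic events SMQ, narrow | Absent |
| Hypersensitivity | Severe, including anaphylaxis | Three SMQs, broad | Named in the label; no rule applies it |

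**2. Does another passage restore the conditions?** I found none. The SAP 11.2 overview and frequency tables use treatment-emergent AESIs with no further filter. For discontinuation and withdrawal the same list names the eCRF form used as source; for AESIs it names none. SAP 11.2 does not refer back to Protocol 9.1.3. The SAP rests on the protocol up to Amendment 2, but the Amendment 3 change list names no AESI change, so the difference in document dates does not explain the mismatch.

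**3. What follows from the text alone?** For bleeding and hypersensitivity, over-inclusion is possible by construction, because the search does not use the deciding attribute (opinion, severity). For thrombosis it depends on whether the narrow query contains terms for localized events, and the documents do not give SMQ contents.

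**4. Can the protocol count be read off other planned output?** Not directly. SAP 11.2 plans a table by system organ class, preferred term and maximum severity, but a subject with two hypersensitivity terms appears under both, so its rows cannot be summed to subjects. The listing of all adverse events would allow a hand count, though its columns are not specified and no such count is prespecified.

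**5. Scale.** SAP section 11 uses the Safety Analysis Set, that is, everyone dosed. SAP 4.4 plans 40 per arm, 80 in total; the 35 per arm are the subjects expected to be evaluable and are not this denominator. Assuming all 80 are dosed, k misclassified subjects in an arm move its proportion by k/40:

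- k = 1: 1/40 = 2.5 points (1/80 = 1.25 points in the overall column)
- k = 2: 2/40 = 5 points
- k = 4: 4/40 = 10 points

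These values of k are illustrative; the documents do not allow k to be estimated.

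**The case against.** The strongest reply is that this is a descriptive phase 2a safety summary. SAP 4.1.1 states no hypothesis, a wide search is a cautious choice for safety, and the planned listings let a reader of about 80 subjects' data recover the narrower count. The absence of any effect on inference stands. So does the value of a wide search, which is a reason to keep it as a supportive table. It does not make an undeclared change of definition acceptable for a primary-endpoint component.

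A reader might also infer more than the documents support:

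- *All three conditions were dropped.* Severity is still named in SAP 11.2 and Table 1. What is missing is a rule that applies it.
- *Localized vascular-access thrombosis will be counted.* This cannot be shown without the SMQ contents. The converse worry, that investigator-reported AESIs coded outside the queries will be missed, has the same limit.
- *Hits will be sorted with treatment known.* The SMQ rule is mechanical and needs no such judgement. SAP section 3 puts analysis decisions before database lock, and Protocol 6.3.3 has the study statistician receive the codes after it.
- *The blinded data review meeting could not take this on.* SAP 9.2 says what the meeting will decide; it does not say it will decide nothing else.
- *Safety monitoring or halting is compromised.* Independent data monitoring committee (IDMC) analyses are left to a charter outside these documents, SAP 4.5.1 allows for listings only, and individual halting under Protocol 3.9.1 uses clinical criteria.

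**Conclusion.** The mismatch is real and should be fixed. Followed exactly, SAP 11.2 gives an AESI number and proportion that need not equal the protocol-defined one: it can include mild hypersensitivity hits and bleeding the investigator did not judge abnormal. SAP section 5 should have declared this and does not.

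The size and direction of any effect cannot be derived, because neither SMQ contents nor expected AESI counts are given. The only firm scale is 2.5 percentage points per misclassified subject in an arm, on the assumption that 40 per arm are dosed. No test, power figure or sample size is affected.

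**What to change.** In SAP 11.2:

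- Make the main AESI summary the number and proportion of subjects in the Safety Analysis Set, in total and by category, with at least one treatment-emergent event that the investigator reported as an AESI under Protocol 9.1.3 and 9.6.2.
- Before database lock and blinded to treatment, query the investigator on SMQ hits not reported as AESIs. The query should go to the investigator because the bleeding condition is that person's opinion; a review panel cannot supply it.
- Apply severe as Protocol 9.1.3 intends it, and count anaphylaxis whatever its recorded grade. Section 9.1.3 does not tie the word to the grades in 9.2, so a filter on the recorded grade alone could drop anaphylaxis graded moderate.
- Do not count non-systemic thrombosis.
- Keep the SMQ-based counts as a separate supportive table, with hypersensitivity hits shown by recorded severity.

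Restore the word abnormal in SAP Table 1, and declare in SAP section 5 that the SMQ search is wider than the protocol definition.

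The cost is SAP wording, one extra table and a blinded reconciliation before lock. Severity is already recorded for every adverse event. The documents do not show an AESI flag in the eCRF, so expedited AESI reports may have to be linked to the adverse event data.

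This fix does not settle the treatment-emergent window: SAP 11.2 ends it with the Treatment and Observation Period, whereas Protocol 10.3.3 sets no end. That needs separate reconciliation.

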4.3 Discontinuation of Study Treatment and Subject Withdrawal

4.3.1 Discontinuation of Study Treatment

Subjects may discontinue study treatment with investigational product at any time at their own request, or at the discretion of the investigator or CSL for safety, behavioral, or administrative reasons.

Subjects who discontinue treatment with investigational product but remain in the study, will be asked to complete additional follow-up assessments or allow data collection as detailed in the [Schedule of Assessments](#). If a subject discontinues investigational product and declines further study procedures / visit participation, the subject will be withdrawn from the study, and attempts will be made to complete and document the Withdrawal Visit assessments. Refer to Section 4.3.2 and Section 4.3.3 for details on handling subject withdrawals.

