10.3.2 Subject Disposition and Characteristics

10.3.2.1 Subject Disposition

Summary tables by treatment group and total population will present:

- The number of subjects enrolled into the study (ie, signed the ICF).
- The number of subjects who prematurely discontinued investigational product.
- The number of subjects who were withdrawn from the study.
- The number of subjects who completed the study.

Reasons for discontinuing the investigational product and withdrawing a subject from the study will be listed by subject.

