7.1 COVID-19 Impact

During the course of this study, the global coronavirus disease 2019 (COVID-19) pandemic is expected to continue. This might impact the study in a variety of ways. This section describes how the potential impact of COVID-19 will be reported.

Subject Disposition: Study Treatment Discontinuation or Study Discontinuation

Subjects who experience either study treatment discontinuation or study discontinuation due to COVID-19 will have the reason captured in the eCRF. On the appropriate eCRF form to record either study medication discontinuation (“End of Treatment” form) or study

discontinuation (“Conclusion of Subject Participation” form), a reason will be selected which includes a field for descriptive text. The reason can be either “Withdrawal by Subject,” “Physician Decision,” or “Other”. The associated free text field entry will include “COVID-19”. When either treatment or the study is discontinued due to an AE or death, the specific corresponding AE is collected. Discontinuations due to COVID-19 related AEs will then be identified based on whether the medical dictionary for regulatory activities (MedDRA) code for the AE is included in standardised MedDRA Query (SMQ): COVID-19 (SMQ (broad)).

Cases of study treatment discontinuation or study discontinuation due to COVID-19 will be included in the summary of subject disposition.

Concomitant Medications

For concomitant medications which are linked to specific AEs, the eCRF collects information to identify the specific AE. As described in the Adverse Events section, relevant AEs will be identified by standardised MedDRA Query (SMQ): COVID-19 (SMQ (broad)). Concomitant medications used to treat COVID-19 associated AEs will be summarized.

Concomitant medications used to treat COVID-19 associated AEs will be flagged in the by-subject listing of prior and concomitant medications.

Adverse Events

AEs associated with COVID-19, which can include a clinically significant laboratory finding, will be reported by investigators following reporting requirements outlined in the CSP. COVID-19 associated AE are identified via MedDRA coding. Relevant AEs will be identified for reporting by standardised MedDRA Query (SMQ): COVID-19 (SMQ (broad)). All COVID-19 associated AEs will be included in standard AE tables.

An overview summary table of COVID-19 associated TEAEs, including number and percentages of subjects as well as the number of events, will be provided for the following:

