An overview summary of TEAEs, including number and percentages of subjects as well as the number of events will be provided including the following:

- Any TEAE;
- TEAEs related to study treatment;
- TEAEs in each severity category;
- TEAEs leading to discontinuation of study treatment (obtained from AE eCRF);
- TEAEs leading to study withdrawal (obtained from “End of Treatment” or “Conclusion of Subject Participation” eCRF);
- TEAEs leading to dose adjustments or dose interruptions;
- Treatment-emergent AESIs;
- Treatment-emergent AESIs related to study treatment;
- Serious TEAEs;
- Serious TEAEs related to study treatment;
- Fatal TEAEs.

COVID-19 associated TEAEs will be included in AE overview table as (as described in [Section 7.1](#)):

- Any TEAE (related/not related);
- Serious TEAE (related/not related);
- Fatal TEAE (related/not related);

- TEAE leading to discontinuation of study treatment (obtained from AE eCRF) (related/not related);
- TEAE leading to dose adjustments or dose interruptions (related/not related);
- TEAE leading to study withdrawal (related/not related);
- TEAE by maximum severity (mild, moderate, severe, missing).

The following frequency tables will be generated for TEAEs, including number and percentages of subjects and the number of events:

- TEAEs by SOC and preferred term;
- TEAEs by preferred term;
- TEAEs by SOC, preferred term, and maximum severity (without number of events);
- Related TEAEs by SOC and preferred term;
- Related TEAEs by preferred term;
- Treatment-emergent AESIs by preferred term;
- Serious TEAEs by SOC and preferred term;
- Related serious TEAEs by SOC and preferred term;
- TEAEs with result in drug discontinuation;
- TEAEs related to COVID-19 infection.

AEs will be presented in summaries by decreasing overall frequency (overall frequency as the number of subjects with that AE beginning with the SOC, followed by preferred term). If 2 AEs have the same overall frequency, the AEs will be ordered alphabetically.

The following by-subject listings will be provided:

- All AEs;
- SAEs;
- AEs leading to study withdrawal or permanent discontinuation of study treatment;
- AESIs by type of AESI;
- Subjects receiving COVID-19 vaccine;
- AEs occurring within 7 days after COVID-19 vaccine administration.

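### The SAP 11.2 source rule for TEAEs leading to study withdrawal admits the form that records stopping of study medication, so read literally it can count subjects who never left the study

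*SAP*

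**What the plan says.** The TEAE overview in SAP 11.2 has two neighbouring rows with different sources. The treatment row is "TEAEs leading to discontinuation of study treatment (obtained from AE eCRF"). The study row is "TEAEs leading to study withdrawal (obtained from “End of Treatment” or “Conclusion of Subject Participation” eCRF"). No further condition is attached to the study row.

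SAP 7.1 explains what the two forms are for. Its sentence runs "On the appropriate eCRF form to record either study medication discontinuation (“End of Treatment” form) or study" and continues "discontinuation (“Conclusion of Subject Participation” form), a reason will be selected which includes a field for descriptive text". The End of Treatment form is thus the record of stopping medication, and the Conclusion of Subject Participation form is the record of leaving the study. The same section adds: "When either treatment or the study is discontinued due to an AE or death, the specific corresponding AE is collected". An adverse event can therefore be linked to either kind of stop.

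Protocol 4.3.1 keeps the two kinds of stop apart. On the first it says: "Subjects who discontinue treatment with investigational product but remain in the study, will be asked to complete additional follow-up assessments". On the second: "If a subject discontinues investigational product and declines further study procedures / visit participation, the subject will be withdrawn from the study". Stopping IP becomes withdrawal only when further participation is also declined. Protocol 10.3.2.1 likewise gives separate disposition lines, one of which is "The number of subjects who prematurely discontinued investigational product", with another for withdrawal from the study.

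**The concern.** The study-withdrawal row accepts a link recorded on a form that, by the SAP's own account, does not record study withdrawal. Stopping dosing while remaining under observation says something about tolerability, but later data are still collected. Leaving the study ends observation. A row labelled as the second but partly filled with the first can report event-driven withdrawals that did not happen.

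Safety is the primary objective, and this overview is the table most readers will look at first. A trial of about 40 subjects per arm gives little room for error: one or two misplaced subjects visibly change a percentage. The misplacement could also differ between arms if IP is stopped for adverse events more often in one of them.

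**Working it through.** The plan states no figure on this point, so there is none to reproduce. The check compares the rule with the possible subject histories and then gives the size per subject.

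**Inputs**
- Source rule for the study row: either form (SAP 11.2).
- Meaning of each form: medication stop or study stop (SAP 7.1).
- Stopping IP without leaving the study is allowed (Protocol 4.3.1).
- Planned size: 40 per arm randomized, 35 evaluable (SAP 4.4).

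**Step 1. Apply three possible rules to each history.** The literal rule takes an event from either form. The second rule uses the Conclusion of Subject Participation form alone. The third keeps both forms but requires that form to show early study discontinuation.

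| History | Literal rule | Conclusion form alone | Both forms, restricted to early leavers |
|---|---|---|---|
| A. Stops IP for a TEAE, stays to Day 92 and the follow-up call | counted | not counted | not counted |
| B. Stops IP for a TEAE and leaves; TEAE on both forms | counted | counted | counted |
| C. Stops IP for a TEAE and leaves; TEAE only on the End of Treatment form, withdrawal by subject on the other | counted | not counted | counted |
| D. Completes dosing, later leaves for a TEAE | counted | counted | counted |
| E. Stops IP for a reason other than a TEAE, stays | not counted | not counted | not counted |

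History A is the error in the literal rule: no study withdrawal took place. History C shows what using the Conclusion form alone could lose. Only the restricted rule handles both.

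**Step 2. Size.** If k subjects in an arm have history A and n are treated, the row is overstated in that arm by 100 × k / n percentage points. With n = 40 (assuming all randomized subjects are treated):
- k = 0: 0
- k = 1: 100 × 1/40 = 2.5
- k = 2: 100 × 2/40 = 5.0
- k = 4: 100 × 4/40 = 10.0

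With n = 35, one subject is 100 × 1/35 = 2.9 points. The values of k are assumptions; the documents give none.

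**Step 3. Agreement with other outputs.** SAP 9.1 counts treated subjects who discontinued the study before Day 64, before Day 92 and before the follow-up call, with reasons. A subject with history A appears in none of these counts but does appear in the SAP 11.2 row. The two outputs therefore disagree by k subjects whenever k is above zero.

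**Step 4. Look for a correcting rule.** SAP 11.2 does not limit the End of Treatment source to subjects who left. The TEAE overview in Protocol 10.3.3 has no study-withdrawal row, so it supplies no overriding definition.

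**The case against.** The strongest reply is that the row's label already sets the criterion. On that reading, the bracketed text only says where to find the event for a subject who has left the study, and a history-A subject is never considered. That reading is possible. The eCRF is not among the documents, so a study-status field on the End of Treatment form cannot be excluded either. What stands is that the miscount depends on literal programming. What does not stand is leaving the text as it is: the SAP mentions no such field and states no such condition, and a programmer would be following the text in taking events from either form.

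A second reply is that the two-form rule has a purpose, namely history C. SAP 7.1 lists withdrawal by subject as a selectable reason, so a true event-driven withdrawal might carry its event only on the End of Treatment form. The documents do not show that sites would record it this way, but the possibility is real. It is why the End of Treatment form should not simply be dropped as a source.

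A third reply concerns importance. Study withdrawal is not among the named primary endpoints, and no test or decision rests on the row. Treatment discontinuation has its own overview row and frequency table, and the SAP 9.1 outputs would let a careful reader detect a wrong count. All of this stands and limits the weight of the point.

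A reader might also infer more than the text supports:
- **That every IP stop is counted as a withdrawal.** Only stops attributed to a TEAE and not followed by leaving the study are affected.
- **That the disposition counts are wrong.** They are defined separately, and nothing here shows an error in them.
- **That the row is certain to be overstated by several points.** The number of affected subjects is unknown and may be zero.
- **That the End of Treatment form serves no other purpose.** SAP 7.1 also uses it for treatment discontinuation in the disposition summary.

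**Conclusion.** The source rule is wrong as written, with limited consequence. SAP 11.2 allows a medication-stop record to define a study withdrawal, contrary to SAP 7.1's account of the forms and Protocol 4.3.1's distinction between the two events. The overstatement is 2.5 percentage points per affected subject at 40 treated per arm, and zero if there are none. It arises only if at least one subject stops IP for a TEAE and remains in the study, and the rule is programmed literally. In that case the row will also differ from SAP 9.1. The documents do not support a claim that a primary endpoint is compromised or that a miscount is certain. The point merits correction because the error would sit in the main safety overview and is easy to prevent before database lock.

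**What to change.** In SAP 11.2:
- Restrict the study-withdrawal row to subjects whose Conclusion of Subject Participation form shows early study discontinuation. Take the event from that form. Use the End of Treatment form only to identify the event for those same subjects, where the first form does not name it.
- For the treatment-discontinuation row, keep the AE eCRF as the source and reconcile it with the End of Treatment form.
- Apply the same restriction to the COVID-19 study-withdrawal row, which at present names no source and could inherit the rule.

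The by-subject listing of events leading to withdrawal or discontinuation combines the two outcomes by design and needs no change.

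The cost is a few lines of SAP text and a small programming change. Both forms are already collected, so no new data are needed.
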